## JHM IRB - eForm A – Protocol

Device	Notes
iPad 	Magnetic cover may increase risk
Headphones 	Bose > Beats, Earbuds
Magnetic toys 	A wide variety, small and large
Cell phone 	Particularly smartphones
Handheld portable games 	Nintendo DS
Vagus nerve stimulator magnet 	Patients with shunts can also have VNS
Transcranial magnetic stimulation 	
Cordless drill 	
Close contact with television 	Direct contact
Amusement park rides 	Magnetic fields or gravitational forces
Direct trauma to valve 	
Magnetic Induction therapy devices 	Prominent in Japan

The frequency with which programmable valves become inadvertently reset as a result of environmental exposure has not been systematically studied and is largely unknown. A literature review by the FDA in 2012, as well as a more recent exhaustive review by our study group, failed to identify a study that carefully evaluated a population of patients with CSF shunts to define the prevalence of inadvertent valve reprogrammings, regardless of symptoms. However, other small studies have clearly shown that IR does occur.

Most previous studies point to IR discovered during clinical evaluations for possible shunt malfunction, not evaluating each patient systematically regardless of their clinical status. Kestle *et al.* found that the Strata valve had an “unexplained change in performance level” 25 times in a total of 22 patients in their 315-patient multicenter study. More recently, Kondageski *et al.* from Great Ormond Street Hospital found that 7 of 24 (29%) patients closely followed with programmable valves were found to have had IR: two were believed to have been related to trauma and 5 had no identifiable cause. Other less comprehensive studies, which likely reported only accidental reprogrammings that were discovered when a shunt malfunctioned, reported IR in 0% and 10% of patients.

Because IR may not cause symptoms severe enough to prompt clinical and/or radiographic evaluation, the lack of a systematic study leaves the true prevalence unknown. IRs have repeatedly been shown to cause symptoms of

Date: 4/19/2016 V.2  
Principal Investigator: [name]  
Application Number: IRB00093490

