### *Study Objectives*

We intend to systematically study our patient population with magnetically susceptible programmable shunts to define the prevalence and consequences of IR, which will enable patients and health care providers to make more informed decisions about the importance of avoiding magnetic fields in household devices

Date: 4/19/2016 V.2  
Principal Investigator: [name]  
Application Number: IRB00093490

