## **JHM IRB - eForm A – Protocol**

whether or not they feel the child is having symptoms of shunt malfunction, as well as their knowledge of the MRI susceptibility of their valve. Specific questions about the frequency and proximity of exposure to devices and circumstances that have previously been associated with IR will also be assessed.

Study personnel will check the valve setting, without divulging any information to the family about where the valve is currently set, in order to minimize patient or family bias when they are completing the questionnaire.

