### *Statistical Considerations*

The statistical analysis will be supervised and performed by [name] and his colleagues at the ACH/JHM CTRO. Demographic and clinical characteristics will be reported by IR status and compared using  $\chi^2$  or Fishers exact tests for categorical measures and t-test or Mann-Whitney U tests for continuous measures.

Aim #1: The frequency of IR will be calculated as the number of hydrocephalic children with Strata CSF shunt valves who had IR divided by the total number of hydrocephalic children with Strata CSF shunt valves.

Aim #2: The association between the field strength of MRI scanning and IR will be determined using unadjusted and adjusted generalized estimating equation models that account for multiple evaluations of participants. IR will be a binary outcome variable (IR present vs IR absent) and the field strength of MRI (3T vs 1.5T) will be the predictor variable. The adjusted model will include potential confounders that will be selected based on prior knowledge of factors established to be associated with IR as well as additional factors with p-value <0.1 in univariate analyses.

Aim #3: We will compare the proportion of patients with signs, symptoms or radiographic changes suggestive of shunt malfunction between the IR and no IR groups using  $\chi^2$  or Fishers exact tests for categorical measures and t-test or Mann-Whitney U tests for continuous measures

Aim #4: The association between devices that may have sufficient electromagnetic charge to affect programmable valves and IR will be determined using unadjusted and

Date: 4/19/2016 V.2  
Principal Investigator: [name]  
Application Number: IRB00093490

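### Aim 3 is the only association aim analysed by crude tests alone, so a link between IR and symptoms could partly reflect confounding, with trauma as one plausible route

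*Combined protocol and SAP*

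**What the plan says.** Under Statistical Considerations in section 7, Aim 3 reads "We will compare the proportion of patients with signs, symptoms or radiographic changes suggestive of shunt malfunction between the IR and no IR groups". The tests named are chi-square or "Fishers exact tests for categorical measures and t-test or Mann-Whitney U tests for continuous measures". No covariate and no model is given.

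The neighbouring aims differ. Aims 2 and 4 each have unadjusted and adjusted GEE models that allow for repeated evaluations, and for both the plan states: "The adjusted model will include potential confounders that will be selected based on prior knowledge of factors established to be associated with IR". Aim 1 is a simple proportion ("The frequency of IR will be calculated as the number of hydrocephalic children with Strata CSF shunt valves who had IR"), so no adjustment is expected there.

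On trauma, the device table in section 3 (Background) has a row "Direct trauma to valve" among the exposures linked to IR. Of the 7 patients with IR in one cited series, "two were believed to have been related to trauma and 5 had no identifiable cause". In section 4, the description of the patient and family questionnaire says that the frequency and proximity of exposure to "devices and circumstances that have previously been associated with IR will also be assessed".

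The stated purpose, under Study Objectives in section 3, is "to define the prevalence and consequences of IR", so that families and clinicians can weigh avoidance of magnetic fields and the need for valve replacement.

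**The concern.** Aim 3 is the aim that bears on the consequences of IR. If a factor makes IR more likely and separately makes signs or symptoms more likely, the IR group will show more symptoms even when the changed setting does no harm. The plan deals with such factors in Aims 2 and 4 and gives no reason for leaving them out of Aim 3.

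Trauma is a plausible example. It precedes the valve reading and is listed with the exposures linked to IR. It may also lead to the Aim 3 outcome by another route. The titles of two case reports cited for the trauma row (references 35 and 39) describe a broken valve after a blow to the head and shunt failure from head banging. At stake is whether a positive result for Hypothesis 3a can be read as an effect of the reset valve, which is how the Background proposes to use it.

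**Working it through.** **Structure of the four aims**

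| Aim | Question | Adjusted model | Repeated evaluations handled |
|---|---|---|---|
| 1 | Frequency of IR | Not applicable | Not stated |
| 2 | MRI field strength and IR | Yes, GEE | Yes |
| 3 | IR and signs, symptoms, imaging | No | No |
| 4 | Device exposure and IR | Yes, GEE | Yes |

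The general comparison of characteristics by IR status at the head of Statistical Considerations could show a trauma imbalance, but would not remove its effect from Aim 3.

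**Illustration of size.** The plan gives no effect size, power or sample size for Aim 3, so there is no figure to reproduce.

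Inputs from the documents:
- Trauma share among IRs of 2/7 (the cited series).
- 1,215 budgeted encounters (Interim Analyses section).
- IR frequency of 5% (used in Sample Size Estimation for precision only). 5% of 1,215 is 60.75, taken as 60 IR and 1,155 no-IR encounters.

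Assumed inputs:
- IR has no effect on symptoms.
- Symptoms in 15% without trauma and 60% with it.
- Trauma before 4% of no-IR encounters.
- Encounters independent.

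Formulas, with q the trauma share in a group:
- Symptom rate = q × 0.60 + (1 − q) × 0.15.
- Crude odds ratio = odds in the IR group / odds in the no-IR group.
- Rejection probability from the two-sided pooled two-proportion z test at 0.05: Φ((d − 1.96·SE₀)/SE₁) + Φ((−d − 1.96·SE₀)/SE₁), where d is the difference in rates, SE₀ the pooled and SE₁ the unpooled standard error.

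At 2/7:
- IR group: 2/7 × 0.60 + 5/7 × 0.15 = 0.279.
- No-IR group: 0.04 × 0.60 + 0.96 × 0.15 = 0.168.
- Odds ratio: (0.279/0.721)/(0.168/0.832) = 1.91.
- d = 0.111, SE₀ = 0.050, SE₁ = 0.059; rejection about 58%.

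Varying the two most influential inputs:

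| Trauma share among IRs | Symptomatic after trauma | IR vs no-IR symptom rate | Crude odds ratio | Rejection |
|---|---|---|---|---|
| 5% | 60% | 17.3% vs 16.8% | 1.03 | 5% |
| 10% | 60% | 19.5% vs 16.8% | 1.20 | 10% |
| 15% | 60% | 21.8% vs 16.8% | 1.38 | 19% |
| 2/7 | 60% | 27.9% vs 16.8% | 1.91 | 58% |
| 2/7 | 25% | 17.9% vs 15.4% | 1.19 | 9.5% |

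The 2/7 share is very imprecise: its exact 95% interval is about 4% to 71%. The 60% versus 15% contrast is a trauma-symptom odds ratio of (0.60/0.40)/(0.15/0.85) = 8.5; 25% versus 15% is (0.25/0.75)/(0.15/0.85) = 1.9.

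A second set of assumptions keeps 2/7, with trauma in 2 to 10% of no-IR patients and baseline symptoms in 10 to 30%. The crude odds ratio is then 1.15 to 1.24 for a trauma-symptom odds ratio of 2, 1.35 to 1.79 for 5, and 1.49 to 2.34 for 10. In every case the odds ratio within trauma strata is 1.00 by construction.

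**The case against.** Hypotheses 3a and 3b are worded as associations, and a crude comparison answers an association question. That is fair as far as it goes. Adjustment becomes necessary when the result is read as a consequence of IR, which is the reading that Study Objectives announces.

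The trauma argument also has limits, and these stand:
- The protocol text never says that trauma produces symptoms without a setting change. The only support is two titles, both about Codman-Hakim valves rather than Strata, and both describing shunt failure rather than symptoms with an intact valve.
- The table row concerns trauma to the valve, not head trauma in general, and the two trauma-related IRs were only believed to be so.
- The route to radiographic findings (Hypothesis 3b) is less clear than the route to symptoms.
- The questionnaire is not shown. A trauma item is implied but not confirmed, and neither is its time window.
- The illustration counts independent encounters, whereas Aim 3 speaks of patients, and Sample Size Estimation expects an average of at least three evaluations each.

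A reader might infer that trauma will create a false link, or that the planned test has a false positive rate near 58%. The documents support neither. That figure needs both the 2/7 share and a strong assumed trauma-symptom association, and the bias nearly vanishes at a 5% share.

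**Conclusion.** The point holds in structure. Aim 3 alone among the association aims has no adjusted analysis, and nothing elsewhere in the plan supplies one. Trauma is a plausible confounder, mainly for Hypothesis 3a, but its second arm is an inference. A crude IR-symptom association could be partly spurious and should not by itself carry a statement on the consequences of IR.

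The size cannot be determined from the documents. Across the main illustration the spurious odds ratio runs from 1.03 to 1.9, resting on assumed symptom rates, an assumed trauma share without IR, a trauma share among IRs drawn from 7 patients or assumed lower, and independence of encounters. These are illustrations, not estimates. The change is worth making because it is cheap and brings Aim 3 into line with Aims 2 and 4.

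**What to change.** - For Hypotheses 3a and 3b, specify unadjusted and adjusted logistic GEE models as in Aims 2 and 4, with the symptom or radiographic finding as response and IR as predictor. This also handles repeated evaluations.
- Pre-specify age and time since the last valve reading as covariates. Add trauma since the last check once the sponsor confirms that the questionnaire records it.
- Add a sensitivity analysis that excludes encounters with reported trauma.
- Keep the crude comparison as descriptive, and base any statement on the consequences of IR on the adjusted estimate.

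Cost: a change of analysis wording if the covariates are already collected. If trauma is not recorded, a questionnaire item is needed. Expect some loss of precision, and keep the covariate list short if IR or symptom events are few.

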## JHM IRB - eForm A – Protocol

adjusted generalized estimating equation models that account for multiple evaluations of participants. IR will be a binary outcome variable (IR present vs IR absent) and the devices (exposed vs non-exposed) will be the predictor variables. The adjusted model will include potential confounders that will be selected based on prior knowledge of factors established to be associated with IR as well as additional factors with p-value <0.1 in univariate analyses.

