### **4) Study Procedures**

#### *Participants*

Patients 21 years of age and younger, with Strata valve CSF shunts, who are being evaluated by the All Children's Hospital (ACH) neurosurgical service as part of standard of care, will be eligible for participation during the three-year enrollment period. Each time an eligible patient has contact with the neurosurgical service their valve will be checked for possible inadvertent reprogramming in the outpatient facilities, emergency department, and inpatient setting. Patients will have their valves checked as part of this study during each encounter. Only patients who were evaluated by the neurosurgical service and returned to their normal environment more than seven days prior to their current encounter will be eligible to have their valves rechecked as part of this study.

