### **8) Risks**

There is a slight risk of loss of confidentiality of the participants' information. Every effort will be used to minimize this risk. Protected health information will be removed prior to data entry with the exception of date of service. Data will be stored on a secure server, and hard data will be stored in locked cabinets.

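### Aim 4 has no term for the time since the last valve reading, so the device odds ratio can be biased in either direction if recorded exposure is related to visit spacing

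*Combined protocol and SAP*

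**What the plan says.** **When valves are checked.** Section 4, Participants: "Each time an eligible patient has contact with the neurosurgical service their valve will be checked for possible inadvertent reprogramming". Spacing therefore follows clinical contact. The only limit is a minimum: a recheck counts only if the child was evaluated by the service and "returned to their normal environment more than seven days prior to their current encounter". Section 5 repeats this. No maximum gap is given, and patients "will be eligible for participation during the three-year enrollment period".

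**How Aim 4 is analysed.** Section 7, Statistical Considerations, specifies unadjusted and "adjusted generalized estimating equation models that account for multiple evaluations of participants", with outcome and predictor defined as "IR will be a binary outcome variable (IR present vs IR absent) and the devices (exposed vs non-exposed) will be the predictor variables". Confounders in the adjusted model are "selected based on prior knowledge of factors established to be associated with IR as well as additional factors with p-value <0.1 in univariate analyses". Neither elapsed time, an offset, person-time nor a time-to-event method appears in the text.

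**What is recorded.** On the questionnaire, section 4 says: "Specific questions about the frequency and proximity of exposure to devices and circumstances that have previously been associated with IR will also be assessed". The questionnaire and data sheet are attachments outside the supplied text. Section 8 says: "Protected health information will be removed prior to data entry with the exception of date of service".

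**The concern.** IR found at an encounter may have happened at any time since the setting was last documented, so the chance of finding it grows with that window. Aim 4 gives an eight-day window and a one-year window the same yes/no outcome. The generalized estimating equations handle correlation between a child's repeated encounters. They do not handle unequal time at risk.

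This matters for the device comparison only if recorded exposure also varies with the interval. There are two plausible routes. If families report exposure since the last visit, a longer window gives more opportunity to be exposed. If they report habits, children who use more devices may also be seen more or less often than others.

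The Aim 4 association is the one on which the study is sized (odds ratio 2.0). Under Interim Analyses, strong associations seen at the six-monthly reviews can end the study early. An artefact of visit spacing could therefore create an association or hide a real one.

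**Working it through.** **The plan's own figures.** Sample Size Estimation gives 996 at 10% exposure for an odds ratio of 2.0, 90% power and two-sided alpha 0.05. This cannot be derived from the stated inputs alone, because the share of encounters with IR and the within-patient correlation are missing. One pair of assumptions that fits is an IR share of 20% and a correlation of about 0.35 over three evaluations, giving a factor (1 + 2 × 0.346)/3 = 0.564. The log-odds-ratio formula then gives 995, 691, 542, 455 and 400, against the stated 996, 692, 542, 455 and 399. Other pairs fit as well, so 996 is not shown to be wrong. It matters here only because an odds ratio of 2.0 is the yardstick.

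**Time at risk.** At an assumed constant hazard of 0.10 per year, the chance of IR is 1 − exp(−0.10 × 8/365) = 0.2% at 8 days and 1 − exp(−0.10) = 9.5% at 365 days, about 43-fold.

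**Crude device odds ratio with no device effect.** Assumptions: half of encounters have a 2-month window and half a 12-month window; the hazard is 1% per month; exposure and IR are independent given the window.

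- P(IR) = 1 − exp(−0.01t): 0.0198 at 2 months, 0.1131 at 12 months, 6.6% overall.
- With exposure e₁ (short) and e₂ (long): P(IR | exposed) = (0.0198e₁ + 0.1131e₂)/(e₁ + e₂), and P(IR | unexposed) = [0.0198(1 − e₁) + 0.1131(1 − e₂)]/(2 − e₁ − e₂).
- For e₁ = 10%, e₂ = 30%: 0.0359/0.4 = 0.0898 and 0.0970/1.6 = 0.0606, so OR = (0.0898/0.9102)/(0.0606/0.9394) = 1.53.

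| Exposure, short / long window | P(IR), exposed | P(IR), unexposed | Crude OR |
|---|---|---|---|
| 10% / 30% | 0.0898 | 0.0606 | 1.53 |
| 15% / 25% | 0.0781 | 0.0635 | 1.25 |
| 18% / 22% | 0.0711 | 0.0653 | 1.10 |
| 20% / 20% | 0.0664 | 0.0664 | 1.00 |
| 30% / 10% | 0.0431 | 0.0723 | 0.58 |

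Keeping 10%/30%, windows of 3 and 12 months give 1.44, and 3 and 6 months give 1.22. With 2 and 12 months, hazards of 0.5% to 2% per month give 1.51 to 1.57. The exposure contrast therefore drives the result more than the hazard does.

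**If exposure means any since the last check.** Give exposure its own constant hazard, independent of IR, with windows of 90, 180 and 365 days in equal shares. Calibrating overall IR to 5–20% and exposure to 10–30%, the null odds ratio is 1.33 to 1.46.

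**Two ways to bring the interval in.** In the 10%/30% case, let the cumulative hazard be proportional to t^k, with value 0.12 at 12 months. A complementary log-log model with a log-interval offset gives a device rate ratio of 0.85 at k = 0.5, 1.00 at k = 1 and 1.09 at k = 1.5. With log interval as a free covariate the device effect is 1.00 in all three. With only two window lengths the free term fits exactly. With many lengths, log interval is exact for this hazard family on the complementary log-log scale and close to it on the logistic scale when IR is uncommon.

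**The case against.** The strongest reply is that the plan already has an adjusted model. In the illustration, short and long windows could coincide with young and older children, and age is an obvious candidate confounder. With IR at 2.0% versus 11.3%, a two-proportion test on that factor passes p<0.1 about 98% of the time with 399 encounters and almost always with 996, treating encounters as independent. Adjusting for it returns an odds ratio of 1.00. Only for windows of 3 and 6 months, where the bias is 1.22, does the screen often miss: it passes about 40% of the time with 399 encounters and a little over 70% with 996. This largely stands, with one condition: interval or a close proxy must be offered to the screen, and the plan does not say so. The prior-knowledge route is weak, because Background describes the frequency of IR as largely unknown. The unadjusted model never contains the term.

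A second reply also stands. The 10% and 30% in Sample Size Estimation are low and high guesses at one overall exposure frequency among patients with IR. They do not describe children with short and long intervals, so the threefold contrast is an assumption of this check. The documents give no distribution of intervals and no data on age and device use.

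A third is that the recall period may already be matched to the interval. It would be set in the attached questionnaire, which is not available here, so its absence cannot be claimed.

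**Conclusion.** The point holds in a conditional form. The plan allows very unequal windows and names no term for them. If recorded exposure is related to the interval, the Aim 4 odds ratio is biased. Under the stated assumptions the null value ranges from 0.58 to 1.53, and it is exactly 1.00 when exposure is unrelated to the interval. The window lengths, hazard and exposure splits are all assumed, so these figures show what can happen and are not a forecast.

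A reader might infer that the device effect will be overstated and that families would be warned off harmless devices. The documents do not support that: nothing in them says which children are seen less often or use devices more, and the reverse pattern would mask a real effect. Nor can 1.53 be taken as the expected size, or the planned adjustment as certain to fail. What remains is that a feature of the design is left to a significance screen that never names it.

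**What to change.** In section 7, Statistical Considerations, Aim #4:

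- Pre-specify log(days since the last documented valve setting) as a covariate with a freely estimated coefficient, forced into the adjusted model whatever its p-value.
- State that this adjusted model is the main Aim 4 result.
- If wanted, add a complementary log-log model with a log-interval offset as a sensitivity analysis only, because it assumes a constant hazard.

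The cost is one model term, plus recording the date of the last documented setting for each child's first encounter. For later encounters the interval can be derived from the dates of service that are already kept. No extra patients or visits are needed. Whether the questionnaire's recall period needs changing cannot be judged without the attachment; the sponsor should check it against the interval as defined here.

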### *Sample Size Estimation*

The sample size estimation for the study is based on the association between IR and devices that may have sufficient electromagnetic charge to affect programmable valves. We estimate that the frequency of exposure to the devices in patients with IR is 10 to 30% and on average each patient may be evaluated at least three times. Based on these estimates, we will need 996 participants to have 90% power at the two-sided alpha level of 0.05 to detect an odds ratio of 2.0 assuming an exposure frequency of 10% (most conservative estimate). If the exposure is 30% we will need 399 participants to obtain the same effect estimate (see Table X below).

Table - Sample size required for different frequencies of exposure, alpha=0.05 (two-sided), power=90% and odds ratio=2.0

Frequency of exposure (%)	10	15	20	25	30
Sample size	996	692	542	455	399

A sample size of 996 will allow us to estimate IR frequency (Aim #1) of 5% with a precision of 1.4% (using a 95%CI).

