## **JHM IRB - eForm A – Protocol**

will be necessary. We budgeted for 1,215 encounters to allow for difficulties we may face related to a multiplicity of encounters per patient, to possible inaccuracies in valve assessment, or due to inevitable human error.

In order to address these difficulties in estimating a necessary sample size, the coordinating center will carefully follow data trends. The study coordinator [name] will work closely with [name] and [name] to report interim results to the ACH study group at least every six months. If strong statistical associations between IR and the other factors being studied can be made with lesser sample sizes, the study will be terminated ahead of schedule and the results will be published promptly.

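### Aim 4 is sized as one device test at two-sided 0.05, but the devices enter as several predictors with no primary exposure and no multiplicity rule.

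*Combined protocol and SAP*

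**What the plan says.** Section 7, Sample Size Estimation: "The sample size estimation for the study is based on the association between IR and devices" that might affect the valve. The calculation is meant "to have 90% power at the two-sided alpha level of 0.05 to detect an odds ratio of 2.0", and 996 is obtained "assuming an exposure frequency of 10% (most conservative estimate". The table there falls from 996 at 10% exposure to 399 at 30%. No device is named, and no number of tests enters.

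Section 7, Statistical Considerations, Aim #4: unadjusted and adjusted generalized estimating equation models with IR as a binary outcome, in which "the devices (exposed vs non-exposed) will be the predictor variables". Aim #2, by contrast, has a single predictor variable, field strength.

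Section 2, Hypotheses 4a to 4c: exposure, frequency of exposure, and distance from the valve, each stated for household items or devices as a class.

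Section 7, Interim Analyses: interim results go to the study group twice a year or more often. Early termination with prompt publication is foreseen on this condition: "If strong statistical associations between IR and the other factors being studied can be made with lesser sample sizes". The plan does not define a strong association.

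Section 10, Benefits: the study is expected to help establish which everyday electronic devices can alter the valves.

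No section names a primary device exposure, a primary model or a multiplicity adjustment.

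**The concern.** Alpha and power are properties of a specified test. Here they are quoted for one test, while the analysis can produce several: one per device, in unadjusted and adjusted form, for exposure, frequency and distance. Without a designated primary exposure, the 0.05 attaches to none of them, and which device result is put forward can be decided after the data are seen.

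This matters because the study is meant to inform advice on household devices and decisions about replacing valves (Section 3, Study Objectives). A false device association would feed into both. It also matters for early termination, because there is no pre-stated exposure against which to judge whether an association is strong.

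**Working it through.** **1. The plan's own figures.** The Aim 1 precision reproduces: 1.96 × √(0.05 × 0.95 / 996) = 0.0135, or about 1.4%. The 996 does not reproduce from the stated inputs alone. Equal-group two-proportion totals at 90% power and two-sided 0.05 are 756 (10% vs 18.2%, odds ratio 2) and 1,318 (10% vs 5.3%, odds ratio 0.5). The plan assumes that "on average each patient may be evaluated at least three times", but gives neither the within-patient correlation nor the IR rate used for power. The whole table row (996, 692, 542, 455, 399) can be matched by an unpooled two-proportion formula with 17% IR in the unexposed and a repeated-measures factor of 0.62. Both values are fitted. The match shows only that the row is consistent with a single test at 0.05 and no multiplicity term. Below, 90% power at 996 is taken at face value.

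**2. Number of tests.** The plan gives none. The device table in the Background has 12 rows. One is direct trauma to the valve, which is not a device, and one is amusement park rides, which is arguable. So m = 10 to 12 is an assumption. Taking the three Aim 4 hypotheses as the family gives m = 3.

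**3. Chance of at least one false finding**, one test each at 0.05, a single look, no true effects, independent tests: 1 − 0.95^m.

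| m | Chance |
|---|---|
| 3 | 14.3% |
| 10 | 40.1% |
| 11 | 43.1% |
| 12 | 46.0% |

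Exposures reported by the same children are likely to be positively correlated, which lowers these figures. With 12 equicorrelated normal test statistics:

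| Correlation | Chance, m = 12 |
|---|---|
| 0.3 | about 40% |
| 0.5 | about 32% |
| 0.7 | about 23% |

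For m = 10 at correlation 0.5 the chance is about 29%. Paired unadjusted and adjusted models, the frequency and distance hypotheses, and the six-monthly looks are not counted and would raise these values.

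**4. Power if Bonferroni over 12 were applied.** The per-test alpha is 0.05/12 = 0.00417, with critical value 2.865. At N = 996, for an exposure whose tabled requirement is n, power = Φ((1.960 + 1.282) × √(996/n) − 2.865).

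| Exposure | Tabled n | Power at 996 |
|---|---|---|
| 10% | 996 | about 65% |
| 15% | 692 | about 85% |
| 20% | 542 | about 94% |
| 25% | 455 | about 97% |
| 30% | 399 | about 99% |

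To keep 90% at 10% exposure, N would be 996 × ((2.865 + 1.282)/(1.960 + 1.282))², or about 1,630.

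**The case against.** The Background table reviews the literature and is not an analysis list. The items actually asked about are in the attached questionnaire, which is not in the text available. Hypotheses 4a to 4c speak of devices as a class, and the sample size uses one exposure frequency, so a single exposed versus non-exposed contrast is not ruled out. A reader might infer that the study tests 12 exposures and has a 46% false-positive risk. The documents do not support that as a fact: the count is not planned, the tests are unlikely to be independent, and a global null sits poorly with items chosen because they have already been linked to valve changes. This part of the objection stands, and the figures are conditional for that reason.

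A reader might also infer that correction would cut power to 65% for every device. That holds only at 10% exposure. By the plan's own table, power stays above 90% from 20% exposure upward. Nor does the text say that any nominal p < 0.05 would end the study: it requires strong associations, left undefined.

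Finally, this is a non-interventional study whose first aim is a frequency, and formal familywise control across observational exposures is partly a matter of judgement. That supports an exploratory label for single devices. It does not remove the need to say which test the stated alpha and power describe. The plural predictors in Aim 4, against a singular one in Aim 2, and the stated benefit of learning which devices matter both point towards device-level conclusions. If a class-level contrast was intended, the plan does not define it.

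**Conclusion.** The concern holds in this form: one association is sized at two-sided 0.05 with 90% power, several device predictors are analysed, and there is no primary exposure and no multiplicity control. If several device tests are run as the text suggests, the plan does not deliver a 5% error rate for the device question.

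The size depends on what the plan leaves open. For 10 to 12 single-device tests, 40% to 46% is the figure under independence with no true effects, at one look and one test per exposure. Moderate to high correlation brings 12 tests down to about 40% to 23%. Three hypotheses give about 14%. All of these exceed 5%. The power figures rest on taking 996 and 90% at face value, which the stated inputs do not allow to be verified.

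This should be corrected before analysis. It does not show that any particular device result would be false.

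**What to change.** Before analysis, name one class-level primary exposure to carry the 0.05 test that sizes the study. One example is any listed household device within 2 inches of the valve since the last check. State which model, unadjusted or adjusted, is primary for it. Check the expected frequency of that exposure against the sample size table.

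Report individual devices as secondary with Holm-adjusted p-values, or as exploratory with confidence intervals only, and list them in the analysis section. Tie any statement about early publication to the primary exposure.

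The cost is mainly wording. Single-device results will carry less weight, and the sizing must be rechecked, since the frequency of a composite exposure is not given in the plan and may lie outside the 10% to 30% range.
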